#### 2.6.1.3 Hypothesis

We hypothesize that talimogene laherparepvec based neoadjuvant therapy will result in an improvement in the NAR score. We recognize that the small sample size and lack of control arm prevent definitive conclusions but the findings will be compared to historical controls and will serve as the preliminary data for designing future, larger trials

### 2.6.2 MRI-based determinants of response, DFS and OS

#### 2.6.2.1 Rationale

Pelvic MRIs are standard of care in the management of resectable rectal cancer to accurately determine stage, evaluate circumferential margins and to determine the extent of required surgery. Emerging data show that baseline MRI features and changes with neoadjuvant therapy correlate with outcomes in patients. However, it is unknown whether pelvic MRIs are able to identify tumor regression with talimogene laherparepvec -based neoadjuvant therapy.

#### 2.6.2.2 Background

In the prospective MERCURY study with a cohort of over 350 patients with resectable rectal cancer, pre-treatment MRI was shown to be predictive of a curative resection based on involvement of the circumferential margin (mrCRM). A subgroup of 111 patients who had both pre- and post-neoadjuvant therapy pelvic MRI were retrospectively evaluated for the prognostic value of tumor regression grade (mrTRG) and mrCRM. Both mrTRG and mrCRM were found to have strong prognostic effects on OS and DFS, as well as for local recurrence (mrCRM only). Based on these data, dedicated pelvic MRIs are performed before and after neoadjuvant therapy in rectal cancer patients routinely as standard of care including at our institution[24].

#### 2.6.2.3 Hypothesis

We hypothesize that rectal adenocarcinoma patients treated with talimogene laherparepvec based neoadjuvant therapy will show improvement in mrCRM involvement and tumor regression and that these changes can be reliably evaluated by pelvic MRIs.

### 2.6.3 Changes in PD-L1 Expression

#### 2.6.3.1 Rationale

Prior studies have shown that radiation and talimogene laherparepvec can both lead to increase in PD-L1 expression in tumors. However, the changes in PD-L1 expression with talimogene laherparepvec based neoadjuvant therapy in rectal adenocarcinoma remains to be determined.

#### 2.6.3.2 Background

Oncolytic viruses often induce interferon (IFN) release in the local tumor microenvironment, and IFN is known to upregulate PD-L1 expression on tumor cells. In fact, preclinical models have validated this approach and several clinical trials are under way. Similarly, radiation independently increases PD-L1 expression by IFN release and other mechanisms. In a preclinical study utilizing an MC-38 colon carcinoma tumors xenograft mouse model, either talimogene laherparepvec or anti-

PD-1 therapy alone induced modest tumor growth inhibition/tumor regressions of contralateral tumors. Correlative studies showed increase in PD-L1 expression in tumors injected with talimogene laherparepvec. In combination, the talimogene laherparepvec injected tumor displayed 8/10 complete regressions and the distant tumors had 2/10 complete regressions[25].

#### 2.6.3.3 Hypothesis

We hypothesize that rectal adenocarcinoma patients treated with talimogene laherparepvec based neoadjuvant therapy will show increase in PD-L1 expression measured by immunohistochemistry in tumor biopsies as compared to baseline.

### 2.6.4 Immune Cell Profiling

#### 2.6.4.1 Rationale

Growing evidence suggests that rectal cancer response to neoadjuvant chemo radiation (CRT) depends on tumor microenvironment and host immune response. Densities of tumor infiltrating lymphocytes (TILs) and peripheral lymphocytes have been correlated with response in this setting.

#### 2.6.4.2 Background

Local and distant antitumor immune responses have been reported in preclinical models and previous clinical studies of talimogene laherparepvec, radiation and the combination of both. For instance, recently, the numbers of pre-treatment peripheral blood helper T lymphocytes and cytotoxic T cells have been shown to be independent predictors of response to radiation in rectal cancer patients. Also, talimogene laherparepvec therapy has been shown to increase the percent of percent of PD-L1+ T cells associated with dramatic local responses in xenograft models of CRC. In a phase II study of talimogene laherparepvec in melanoma, biopsy of responding lesions suggested an association between response and presence of interferon  $\gamma$ -producing MART-1-specific CD8+ T cells and reduction in CD4+FoxP3+ regulatory T cells[26].

#### 2.6.4.3 Hypothesis

We hypothesize that the local and systemic immune effects of talimogene laherparepvec may cooperate with neoadjuvant therapy to increase locoregional control in rectal cancer. We propose to quantify changes in a) tumor immune cell infiltration and to characterize subtypes of the immune cells by IHC b) peripheral T cell subpopulations by flow cytometry with talimogene laherparepvec injection and radiation in rectal cancer.

## 2.6.5 Pharmacodynamic Markers of Talimogene Laherparepvec

### 2.6.5.1 Rationale

Talimogene laherparepvec has previously been shown to be feasible to be used for injection into multiple tumor types including melanoma, SCCHN and pancreatic cancer. However, the feasibility and efficacy of talimogene laherparepvec delivery into rectal adenocarcinoma remains to be determined. The current trial provides a valuable opportunity to evaluate this.

### 2.6.5.2 Background

Prior studies have shown that all patients seronegative for HSV strongly seroconvert 3-4 weeks after their first dose that for seropositive patients, trend was an increase in anti-HSV antibody with each injection that eventually plateaued. GM-CSF expression in injected tumors has also been shown to increase post-injection that seemed to be dose related in a phase I study increasing from dose level  $10^6$  to  $10^7$ . This phase I and other phase II studies have also established talimogene laherparepvec DNA as a reliable marker for talimogene laherparepvec infection and replication within injected lesions.

### 2.6.5.3 Hypothesis

We hypothesize that endoscopic injection of talimogene laherparepvec into rectal adenocarcinoma is an effective delivery method leading to adequate infection and proliferation of the oncolytic virus within the tumor cells as demonstrated by increase in serum HSV antibody titers (measured by ELISA), GM-CSF (IHC) and talimogene laherparepvec DNA (qRT PCR) in tumor samples

## 3. PATIENT SELECTION

### 3.1 Inclusion Criteria

3.1.1 **For dose escalation:** Patients must have A) histologically or cytologically confirmed low lying (up to 6 cm of anal verge) rectal adenocarcinoma eligible for radiation therapy to rectal tumor, B) If the treatment is palliative in the metastatic setting, no additional requirements for tumor size or nodal involvement is needed. C) If the treatment is in the neoadjuvant setting, the tumor must ALSO be high-risk locally advanced rectal cancer defined as T3-4, N+, and/or at risk for a positive radial margin (as determined by the surgeon)

3.1.2 **For dose expansion:** Patients must have A) histologically or cytologically confirmed rectal adenocarcinoma eligible for radiation therapy to rectal tumor irrespective of location from anal verge, B) If the treatment is palliative in the metastatic setting, no additional requirements for tumor size or nodal involvement is needed. C) If the treatment is in the neoadjuvant setting, the tumor must ALSO be high-risk locally advanced rectal cancer defined as T3-4, N+, and/or at risk for a positive radial margin (as determined by the surgeon)

3.1.3 Age  $\geq$ 18 years. Because no dosing or adverse event data are currently available on the use of talimogene laherparepvec in combination with chemotherapy in patients  $<$ 18 years of age

3.1.4 ECOG performance status  $\leq$  2 (Karnofsky  $\geq$ 60%, see Appendix A).

3.1.5 Patients must have normal organ and marrow function as defined below:

- Absolute neutrophil count (ANC)  $\geq$ 1.5x10^9/L
- Hemoglobin  $\geq$ 9 g/dL
- Platelets  $\geq$ 100,000 x10^9/L
- Serum bilirubin  $\leq$ 1.5x institutional upper limit of normal (ULN)  
(except patients with Gilbert's Syndrome, who can have total bilirubin  $<$  3 mg/DL)
- Aspartate aminotransferase (AST) and alanine aminotransferase (ALT)  $\leq$ 2.5x institutional ULN
- Serum creatinine  $\leq$ 1.5 mg/dL *OR* calculated creatinine clearance (Cockcroft-Gault formula)  $\geq$ 50 mL/min *OR* 24-hour urine creatinine clearance  $\geq$ 50 mL/min
- Prothrombin time (PT)/International normalized ratio (INR) and partial thromboplastin time (PTT)  $\leq$ 1.5x institutional unless the subject is on anticoagulant therapy (If the subject is receiving anticoagulant therapy, PT, and aPTT must be within therapeutic range of intended use of anticoagulants)

3.1.6 Patients must have signed informed consent indicating that they are aware of the investigational nature of the study, and are aware that participation is voluntary. Patients must be made aware of their other treatment options.

3.1.7 Talimogene laherparepvec, as well as other therapeutic agents used in this trial including radiation and 5-FU, may cause fetal harm when administered to a pregnant woman.

Women of childbearing potential (WOCBP) is defined as any female who has experienced menarche and who has not undergone surgical sterilization (hysterectomy or bilateral oophorectomy) or who is not postmenopausal. Menopause is defined clinically as 12 months of amenorrhea in a woman over 45 in the absence of other biological or physiological causes.

WOCBP and men must agree to use adequate contraception (hormonal or barrier method of birth control; abstinence) prior to study entry, during the study participation, and for four months after the last dose of the drug.

WOCBP must have a negative serum pregnancy test within 72 hours prior to enrollment and agree to use effective contraception throughout the treatment period and for 4 months after the last dose of study treatment. Should a woman become pregnant or suspect she is pregnant while she or her partner is participating in this study, she should inform her treating physician immediately.

3.1.8 Ability to understand and the willingness to sign a written informed consent document.

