#### 4.4 General Guidelines

Following registration, patients should begin protocol treatment within 7 business days.\* Issues that would cause treatment delays should be discussed with the Principal Investigator. If a patient does not receive protocol therapy following registration, the patient's registration on the study may be canceled. The Study Coordinator should be notified of cancellations as soon as possible.

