### **SPECIAL INSTRUCTIONS:**

Initial agent supplies may be requested only when subject enrollment onto the study is confirmed.

There will be NO next day delivery of Talimogene laherparepvec requests available. Sites must plan agent ordering and study subject treatment accordingly.

Agent order requests received on Monday, Tuesday, or Wednesday of the week, will be shipped on Tuesday, Wednesday and Thursday, respectively. Agent order requests received on Thursday or Friday of the week will be shipped on Monday of the following week. There will be no exceptions to this planned schedule. Sites should also consider planned Federal Government holidays when submitting agent requests and scheduling study subject treatment.

Talimogene laherparepvec will be shipped on dry ice. Only one strength of the agent will be in a single shipping container. You may receive multiple shipping containers for a single strength depending on the number vials being shipped. Upon receipt of the agent supplies, the site has 90 seconds to verify the contents and place the agent supplies in the  $-80^{\circ}\text{C}$  ( $+\text{- }10^{\circ}\text{C}$ ) freezer (see Appendix...) once the inner shipping container lid is opened and the supply exposed to room temperature. Record exposure time in the temperature exposure tracking log (see Appendices F & G). The log must be retained with your study records. If exposure time exceeds 90 seconds, quarantine the agent supplies in the  $-80^{\circ}\text{C}$  ( $+\text{- }10^{\circ}\text{C}$ ) freezer and call PMB immediately at [contact] for guidance.

8.1.3.2 Agent Inventory Records – The investigator, or a responsible party designated by the investigator, must maintain a careful record of the receipt, dispensing and final disposition of all agents received from the PMB using the appropriate NCI Investigational Agent (Drug) Accountability Record (DARF) available on the CTEP forms page. Store and maintain separate NCI Investigational Agent Accountability Records for each agent, strength, formulation and ordering investigator on this protocol.

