## 10. STUDY CALENDAR

Baseline evaluations (including laboratory tests) need not be repeated at start of protocol therapy if done within 1 week. Scans, x-rays must be done  $\leq$ 4 weeks prior to the start of therapy. In the event that the patient's condition is deteriorating, laboratory evaluations should be repeated within 48 hours prior to initiation of the next cycle of therapy. **On-study tests/visits** that must occur within a defined time frame shall have a standing window of allowance that is equal to +/- 2 days for any laboratory testing and +/- 4 days for any re-staging/disease assessment criteria. Surgery in eligible patients may occur within a window of +/- 2 weeks

	Pre-Study	Week 0	Wk 1	Wk 2	Wk 3	Wk 4	Wk 5	Wk 6	Wk 7	Wk 8 g	Wk 9/10 g	Wk 12/13 – 19/20 g m	Wk 27 - 36	Wk 27 & beyond f	Off Study c
TALIMOGENE LAHERPAREPVEC b		X			X		X		X						
FOLFOX A			X		X		X		X			X			
RT k												X			
Surgery n													X		
Informed consent	X														
Demographics	X														
Medical history	X														
Concurrent meds h	X		X-----									X			
Physical exam	X	X	X		X		X		X	X	X	X			X
Vital signs	X	X	X		X		X		X	X	X	X			X
Height	X			X		X		X	X	X	X	X			
Weight	X		X		X		X		X	X	X	X			X
Performance status	X		X		X		X		X	X	X	X			X
CBC w/diff, plts	X	X	X		X		X		X	X	X	X			X
PT / INR / aPTT d	X	X													
Serum chemistry a	X	X	X		X		X		X	X	X	X			X
Tumor Markers e	X												X		
EKG (as indicated)	X														
Adverse event evaluation h	X		X-----									X			X
Tumor measurements	X		In addition to baseline, tumor measurements will be obtained prior to surgery (wk 21-25). Documentation (radiologic) must be provided for patients removed from study for progressive disease.												X
Radiologic evaluation	X		In addition to baseline, radiographic evaluation will be obtained prior to surgery (wk 21-25).												X
B-HCG	X b														
CORRELATIVE STUDIES															
Archival Tissue	X														

Pelvic MRI	X										X	
Tumor Biopsies i			X j					X			X	
Peripheral Blood l	X							X			X	
	A:	FOLFOX: Dose as assigned; administration schedule										
	B:	TALIMOGENE LAHERPAREPVEC: Dose as assigned; administration schedule										

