	a:	Albumin, alkaline phosphatase, total bilirubin, bicarbonate, BUN, calcium, chloride, creatinine, glucose, LDH, phosphorus, potassium, total protein, SGOT [AST], SGPT [ALT], sodium.										
	b:	Serum pregnancy test (women of childbearing potential).										
	c:	Off-study evaluation.										
	d:	At baseline and subsequently as required per treating physician's discretion										
	e:	Tumor markers include CEA and CA 19-9 at baseline, if above normal, repeat within 1 week of day 1 of radiation and with presurgical evaluation										
	f:	Chemotherapy regimen / dosing / schedule, imaging and follow up post-surgery per treating physician's discretion										
	g:	Evaluation by any involved provider (medical oncology / surgical oncology and / or radiation oncology)										
	h:	Adverse event evaluation until 4 weeks out of surgery										
	i:	Optional										
	j:	In patients without adequate archival tissue										
	k:	Radiation will be 25 Gy over 5 fractions.										
	l:	Refer to Section 9 for tube types and volumes.										
	m:	On day 1 of each cycle of FOLFOX										
	n:	In those deemed needing surgical resection per clinical evaluation; not mandatory per protocol										

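### The pregnancy test is timed to enrollment, not to first dose: it can be up to 7 days old at the first talimogene injection and nominally about 14 at first FOLFOX, which a cheap Week 0 test would tighten

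*Combined protocol and SAP*

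**What the plan says.** Section 3.1.7 sets the eligibility test: "WOCBP must have a negative serum pregnancy test within 72 hours prior to enrollment". In the Section 10 calendar the B-HCG row has one mark, at Pre-Study. Its footnote b describes the test, "Serum pregnancy test (women of childbearing potential", and gives no timing and no repeat. Physical exam, blood count, coagulation tests and serum chemistry are marked again at Week 0; B-HCG is not.

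Three other provisions decide how old the test can be at first dose:

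- Section 4.4: "Following registration, patients should begin protocol treatment within 7 business days". It adds: "Issues that would cause treatment delays should be discussed with the Principal Investigator".
- Section 10: "Baseline evaluations (including laboratory tests) need not be repeated at start of protocol therapy if done within 1 week".
- Section 8.1.3.1, Special Instructions: "Initial agent supplies may be requested only when subject enrollment onto the study is confirmed". There is no next-day delivery, and "Agent order requests received on Thursday or Friday of the week will be shipped on Monday of the following week".

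The first talimogene injection is at Week 0 and the first FOLFOX at Week 1 (Section 5.1).

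**The concern.** Section 3.1.7 says that talimogene, radiation and 5-FU can harm a fetus. Section 3.2.14 is more specific. It reports no embryo-fetal effects of talimogene in animals, notes that adequate studies in pregnant women are lacking, and places the high risk on 5-FU, oxaliplatin and radiation. It also bars pregnant women from study treatment, not only from enrollment. A check on that exclusion is worth most just before treatment starts, yet the only scheduled test is counted back from enrollment.

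The plan has other safeguards: agreed contraception before and during the study, exclusion of women planning pregnancy, condom use while on treatment, immediate reporting of a suspected pregnancy, and pregnancy as a reason to stop treatment (Sections 3.1.7, 3.2.14 and 5.5). None of these would reliably detect an early pregnancy that the enrollment test came too soon to show.

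What is at stake is fetal safety. Sample size, the dose-escalation rules and their operating characteristics are unaffected.

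**Working it through.** The plan states no test age at first dose, so there is no figure to reproduce. The check is calendar arithmetic.

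**Inputs.** Test to enrollment: at most 72 hours = 3 days (3.1.7). Enrollment to first treatment: 7 business days (4.4). Age at which a baseline laboratory test need not be repeated at start of therapy: up to 7 days (10). Week 0 to Week 1: 7 days, nominal (5.1).

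**Reading A: the one-week rule covers B-HCG.** The rule names laboratory tests, so this is the natural reading.

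- At the first injection: maximum 7 days. This is reachable with a test 3 days before enrollment and a start 4 days after it (3 + 4 = 7), well inside the window that Section 4.4 allows.
- At first FOLFOX: 7 + 7 = 14 days. This is nominal. Sections 2.4 and 5.1 also describe the first injection as in week 1 before FOLFOX begins, which allows a shorter gap.

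**Reading B: the rule does not cover B-HCG, because it has no Week 0 mark.** Without holidays, 7 business days is 9 calendar days after a Monday to Wednesday registration and 11 after a Thursday or Friday one.

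- At the first injection: 3 + 9 = 12 or 3 + 11 = 14 days.
- At first FOLFOX: 12 + 7 = 19 or 14 + 7 = 21 days.
- A holiday or a delayed start would lengthen these, since the 7 business days is a recommendation.

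**Is an age above 72 hours unusual?** Assume drug is ordered on the enrollment day and transit takes 1 day; the documents give no transit time.

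| Enrollment day | Ships after | Earliest arrival | Test drawn on enrollment day | Test drawn 3 days before |
|---|---|---|---|---|
| Mon–Wed | 1 day | 2 days | 2 days old | 5 days old |
| Thu | 4 days | 5 days | 5 days old | 8 days old |
| Fri | 3 days | 4 days | 4 days old | 7 days old |

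With newly ordered drug, an age above 72 hours is therefore an ordinary outcome. After a Thursday or Friday enrollment it occurs even with a same-day test. Under Reading A the 8-day case would be retested. Stock already at the site could shorten the lag for later patients.

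**With the fix.** At injection: 3 days. At first FOLFOX: 3 + 7 = 10 days, or 3 with a second test within 72 hours before FOLFOX.

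**Women concerned.** Planned enrollment is 10 women among 21 patients (Section 13.2). Assume that the completed first cohort had its planned 3 patients.

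- If dose level 2 is the MTD, 15 patients are treated there: 15 × 10/21 = 7.1.
- Up to the cap of 21, 18 places remain (21 − 3): 18 × 10/21 = 8.6.

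That is about 7 to 9 women; how many are of childbearing potential is not stated.

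**The case against.** Enrollment is a normal anchor for an eligibility test. Section 4.3.2 has sites verify eligibility before registration, and other criteria count back from enrollment too (recent immunosuppression, live vaccines). On the natural reading the plan already limits the test to 7 days at injection, so the gain there is from 7 days to 3, and its benefit cannot be quantified. A repeat test could itself miss a very early pregnancy. All of this stands, and it is why the point is an improvement and not a defect.

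The firm requirement also sits at talimogene, while Section 3.2.14 places the high risk elsewhere. By radiation in weeks 9/10 a Week 0 test is about nine weeks old, and FOLFOX continues to weeks 18/19. That is fair: the change addresses the start of treatment only, and later exposure still rests on contraception and reporting. Week 0 remains the right place for the firm test, because a positive result there stops treatment before any study agent is given.

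A reader might infer that the plan breaks a 72-hour commitment, or that its sections contradict each other. Neither is so: no section promises a 72-hour-old test at first dose, and the rules can all be followed together. A reader might also take the two- or three-week ages as the plan's limits. They arise only under the less natural reading of Section 10.

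**Conclusion.** The point holds as a cheap safety improvement. The test is tied to enrollment, and a result more than 72 hours old at first injection is permitted and will be common with newly ordered drug. The maximum age is 7 days at injection on the natural reading of Section 10, and nominally about 14 at first FOLFOX if Week 0 and Week 1 are a full 7 days apart. Footnote b does not settle whether the one-week rule applies to B-HCG, so two sites could work to different limits; on the other reading the age at injection is about 12 to 14 days.

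These are ages of a test result. They should not be read as a rate of missed pregnancies, for which the documents give no basis. The 7 to 9 women are an upper bound on those affected, and rest on the planned female share and a first cohort of 3.

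**What to change.** Keep the eligibility test. Add to Section 3.1.7 and to calendar footnote b, with a B-HCG mark at Week 0:

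*Women of childbearing potential need a negative serum pregnancy test within 72 hours before the first talimogene injection. One test may serve for eligibility and for this requirement. B-HCG is exempt from the one-week no-repeat allowance.*

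Optionally, add B-HCG to the Week 1 laboratory tests before FOLFOX, since Section 3.2.14 places the high fetal risk on 5-FU, oxaliplatin and radiation.

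**Cost.** One addition in each of two places and one calendar mark (two with the Week 1 option). Usually this means one extra serum assay per woman of childbearing potential, or two with Week 1. The Week 0 sample can often be drawn with scheduled blood, but where the one-week rule would have waived the Week 0 laboratory tests it needs a separate draw. The result must be back before the injection, which may mean a wait on the day or an earlier visit.
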